14.2. Reporting requirements

14.2.1. AE reporting

AE's will be recorded from the first drug administration until the end of the study, as defined in section 5.2.

Special attention will be given to those subjects who have discontinued the study for an AE, or who experienced a severe or a serious AE. All AE's should be recorded in the patient's file and in the CRF.

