4.2. Secondary End Points + Time Points

- to study if early intervention with sargramostim is safe (number of AEs/SAEs)

Although sargramostim has been given previously by inhalation to patients with ARDS and interstitial lung disease, data on safety in patients with COVID-19 infection are currently lacking. Since we are randomizing against 5 days of no sargramostim treatment, comparison of AEs and SAEs between group A and group B will be very informative.

-to study if early intervention with inhaled sargramostim affects clinical outcome defined by Length of hospital stay

Mean and median change in 6-point ordinal scale change between day 1, day 6

Mean and median change in clinical sign score between day 1 and day 6

Time to clinical sign score <6 maintained for 24h

Mean and median change of SOFA score between day 1 and day 6 or between day 1 and day 10.

Mean and median change NEWS2 score between day 1 and day 6 or between day 1 and day 10.

Time to NEWS2 score less than 2 for at least 24h

- to study if early intervention with sargramostim affects the rate of nosocomial infection

Patients with viral respiratory infection are at risk of secondary bacterial infections. As part of routine clinical care, sputum samples will be collected in patients suspected of secondary bacterial pneumonia, and checked for the presence of bacteria.

-to study if early intervention with inhaled sargramostim affects progression to mechanical ventilation and/or ARDS

Decreasing oxygenation often leads to the need for non-invasive or invasive mechanical ventilation, and if severe enough to a diagnosis of ARDS. We will therefore as a secondary endpoint also study if early intervention with inhaled sargramostim prevents progression to criteria-defined ARDS (according to the American-European Consensus Conference (AECC) diagnostic criteria for ARDS: acute onset; ratio of partial pressure of arterial oxygen to fraction of inspired oxygen (PaO_2/FiO_2) of 200 or less, regardless of positive end-expiratory pressure; bilateral infiltrates seen on frontal chest radiograph; and pulmonary artery wedge pressure of 18 mm Hg or less when measured, or no clinical evidence of left atrial hypertension), requiring high-flow oxygen devices, non-invasive mechanical ventilation, mechanical ventilation, by measuring the day from admission when this diagnosis is made or therapies are initiated.

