7.1. Subjects

7.1.1. Number of subjects and planned recruitment rate

There is a large number of COVID-19 infected patients that are currently being hospitalized across the globe. In just 9 days time, our COVID-19 ward at Ghent University Hospital has admitted 25 confirmed cases, of which a significant portion (50%) already fulfill eligibility criteria for the current proposed protocol. Similar numbers of patients are currently being seen in all centers. We therefore believe that given the current ascending part of the epidemiology curve, with numbers of patients rising sharply, there will be no shortage of patients that are eligible.

The number of subjects that will be included in this study is: 80.
These are divided into following sub-groups:

Group A : active **sargramostim** treatment group, treatment for initial 5 days, no deterioration after 5 days

Number of patients : 40

Group B : control group : no treatment with sargramostim in first 5 days

Number of patients : 40

Group C and D :

Data from the Wuhan COVID-19 epidemic show that patients that deteriorate are facing a prolonged period of mechanical ventilation. Therefore, from day 6 onwards, progressive patients in the active group will have the option to receive an additional 5 days of IV sargramostim 125mcg/m² body surface area once daily, based on the treating physician's assessment. This group will be called group C. It is estimated that some 30% of patients might deteriorate and require non-invasive or invasive mechanical ventilation, giving potentially rise to 12 patients that progress from group A to group C, if the clinician decides to move forward with the drug.

In the control group progressing to requiring non-invasive or invasive mechanical ventilatory support, from day 6 onwards, the treating physician will have the option to initiate IV sargramostim 125mcg/m² body surface area once daily for 5 days. This group will be called group D. It is estimated that some 30% of patients might deteriorate to mechanical ventilation or ARDS, giving potentially rise to 12 patients that progress from group A to group C, if the clinician decides to move forward with the drug

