8.1.8. Known side effects of the medication

To date, there have been no new safety signals associated with LEUKINE® (sargramostim). Observed side effects with aerosolized LEUKINE® at 250mcg dose and in at least one evaluation have included: bronchospasm, cough, dyspnea, a decrease in vital capacity and/or forced expiratory volume associated with bilateral infiltrates, pleural effusions, increased phlegm, throat irritation, and back pain.

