14.1. Definitions

Term	Definition
Adverse Event (AE)	Any untoward medical occurrence in a subject to whom a medicinal product has been administered, including occurrences which are not necessarily caused by or related to that product.
Unexpected Adverse Event	An adverse event, the nature or severity of which is not consistent with the applicable product information (e.g., Investigator's Brochure for an unapproved investigational product or package insert/summary of product characteristics for an approved product).
Adverse Reaction (AR)	
An untoward and unintended response in a subject to an investigational medicinal product which is related to any dose administered to that subject.
 
The phrase "response to an investigational medicinal product" means that a causal relationship between a study medication and an AE is at least a reasonable possibility, i.e. the relationship cannot be ruled out.
 
All cases judged by either the reporting medically qualified professional or the Sponsor as having a reasonable suspected causal relationship to the study medication qualify as adverse reactions.

Serious Adverse Event (SAE)	
A serious adverse event is any untoward medical occurrence that:
 
 • results in death • is life-threatening • requires inpatient hospitalisation or prolongation of existing hospitalisation • results in persistent or significant disability/incapacity • consists of a congenital anomaly or birth defect 
Other 'important medical events' may also be considered serious if they jeopardise the subject or require an intervention to prevent one of the above consequences.
 
NOTE: The term "life-threatening" in the definition of "serious" refers to an event in which the subject was at risk of death at the time of the event; it does not refer to an event which hypothetically might have caused death if it were more severe.

Serious Adverse Reaction (SAR)	An adverse event that is both serious and, in the opinion of the reporting Investigator, believed with reasonable probability to be due to one of the study treatments, based on the information provided.

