14.5. Events, excluded from reporting

COVID-19 infection is a very recent syndrome, on which few data are available. Normal symptoms and natural disease course symptoms that will not be reported as adverse events are dyspnea, coughing, malaise, fever, drop in oxygen saturation, progression to respiratory failure, progression to ARDS, severe drop in blood pressure in the ICU, progression to multi-organ failure.

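### Non-serious adverse events have no recording window common to both arms, and the reporting exclusions overlap with two observed effects of the inhaled drug

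*Protocol*

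**What the plan says.** **Window.** Protocol 14.2.1: adverse events "will be recorded from the first drug administration until the end of the study". Section 14.1 defines an adverse event as "Any untoward medical occurrence in a subject to whom a medicinal product has been administered".

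**Exposure of controls.** Section 7.1.1 describes "Group B : control group : no treatment with sargramostim in first 5 days". For controls who progress to ventilatory support, "from day 6 onwards, the treating physician will have the option to initiate IV sargramostim".

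**Planned comparison.** Section 4.2 makes safety the first secondary endpoint. It notes that safety data in COVID-19 are lacking and, because randomisation is against five days without sargramostim, concludes that "comparison of AEs and SAEs between group A and group B will be very informative".

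**Other safety text.** Section 1.6 has safety data collected in all patients. The schedule in 9.4 marks an (S)AE inquiry at screening and at follow-up, with no restriction to one arm. Section 14.2.2 requires all SAEs over the entire study period.

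**Exclusions.** Section 14.5 lists normal and natural-course symptoms "that will not be reported as adverse events are dyspnea, coughing, malaise, fever, drop in oxygen saturation, progression to respiratory failure", and continues with ARDS, severe blood pressure drop in the ICU and multi-organ failure. Section 8.1.8 gives the effects observed with the aerosolised drug, beginning with "bronchospasm, cough, dyspnea, a decrease in vital capacity and/or forced expiratory volume".

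**The concern.** There are two separate faults.

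The first is the anchor. A comparison of event counts between randomised arms needs a window that opens at the same point in both. First drug administration is an event that the active arm has on Day 1 and controls do not have in days 1-5. Sites that follow 14.2.1 to the letter would collect non-serious events on one side only. Sites that follow 9.4 would collect them on both. In an open-label trial that difference in practice goes straight into the comparison, and no later analysis can recover events that were never recorded.

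The second is the exclusion list. Two of the symptoms kept out of AE reporting are effects that the protocol itself associates with inhaling this drug. A rise in either on the active arm would not show in an AE table.

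What is at stake is a secondary objective. The primary oxygenation endpoint is not touched.

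**Working it through.** **1. The protocol's own figure.** Section 7.1.1 expects some 30% of controls to deteriorate and gives 12 patients. (The sentence names groups A and C, but it stands in the control-group paragraph, so I read it as B to D.) Check: 0.30 × 40 = 12. It reproduces.

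**2. Controls with an AE window under the literal rule.**
- Days 1-5: 0 of 40, since none is given sargramostim.
- From day 6: at most about 12 of 40 (30%), if every progressing control is treated.
- Never: 40 − 12 = 28 of 40 (28/40 = 70%).
- With a start at randomisation or Day 1: 40 of 40.

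**3. Size of the possible distortion.** The protocol gives no AE rate, so the rates here are assumptions. Suppose the true risk p of a non-serious AE in days 1-5 is the same in both arms, and that sites apply 14.2.1 literally. Recorded counts are then x = 40p on active and 0 on control. With 40 per arm, the two-sided Fisher exact p-value for x versus 0 is 2 × C(40, x) / C(80, x).

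| Assumed risk in both arms | Recorded, active vs control | Fisher p |
|---|---|---|
| 10% | 4 vs 0 | 0.12 |
| 20% | 8 vs 0 | 0.005 |
| 30% | 12 vs 0 | 0.0002 |

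The recorded risk difference equals p, while the true difference is zero.

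**4. Which events the window affects.** The SAE entry in 14.1 has no dosing condition, and 14.2.2 runs over the whole study. Serious events therefore have a common window, and the distortion in step 3 applies to non-serious events only.

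**5. Overlap of the two lists.** Section 8.1.8 has eight items: bronchospasm; cough; dyspnea; reduced vital capacity or forced expiratory volume with infiltrates; pleural effusions; increased phlegm; throat irritation; back pain. Section 14.5 has nine: dyspnea; coughing; malaise; fever; drop in oxygen saturation; respiratory failure; ARDS; severe blood pressure drop in the ICU; multi-organ failure. The items common to both are cough and dyspnea, 2 of 8. The other six remain reportable.

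**6. Serious cases of excluded events.** Section 14.2.2 asks for all SAEs. Section 14.5 says that its listed events are not reported as adverse events and sets no limit for seriousness. Section 14.1 defines a serious adverse reaction as a kind of adverse event. A serious dyspnea judged related to the drug is thus required by 14.2.2, while 14.5 can be read as removing it. The text does not say which prevails.

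**The case against.** The strongest reply is that nobody would run the trial this way. Section 1.6 speaks of all patients, 9.4 shows an inquiry from screening, 14.4 asks for all AEs per subject, and 4.2 presupposes that control events are recorded. This has force: zero recorded events in controls is what one sentence implies, not a forecast of what sites will do. But these passages contradict 14.2.1 without replacing it, and 14.2.1 is where the start of recording is set.

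A reader might infer that 14.1 independently removes controls. It does not: it speaks of a medicinal product, whereas the adverse-reaction entry says investigational medicinal product, and controls do receive standard-of-care drugs. Reading the first drug administration in 14.2.1 equally broadly would not help, because the start could then precede randomisation and differ between patients.

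A reader might also infer that the whole safety comparison is invalid, or that respiratory harm from inhalation cannot be seen at all. Neither is supported. SAEs have a study-wide window. Mortality and progression to ventilation or ARDS are secondary endpoints in both arms. Six of the eight listed effects stay reportable. Cough and shortness of breath are graded 0-3 in the clinical sign score, and saturation is measured daily during treatment. The exclusion applies to both arms, so it can hide a signal but does not itself create an excess on active. What these measures do not supply is an event record with causality and timing relative to nebulisation.

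Finally, 14.5 is framed as natural-course symptoms, so an event provoked by nebulisation arguably falls outside it. That is a fair reading, but the text gives no way to tell the two apart.

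**Conclusion.** The point holds for non-serious adverse events. As written, 14.2.1 gives no recording window common to groups A and B: 0 of 40 controls are covered in days 1-5 and about 28 of 40 are never covered, on the protocol's 30% estimate. If applied literally, the comparison is biased towards excess events on the active arm. With an assumed equal true risk of 20%, it would show 8 versus 0. The size depends on that assumed risk and on how sites resolve the conflict with 1.6 and 9.4. The window does not affect the SAE comparison.

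The second fault is narrower. Section 14.5 withholds two of the eight effects listed in 8.1.8 from AE reporting, in both arms, and leaves it open whether serious cases fall under 14.2.2. A reader might further infer that the data safety monitoring board would be shown distorted tables. The protocol says only that a board is foreseen and describes no tables, so this cannot be concluded.

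**What to change.** - **14.2.1:** record AEs from randomisation (or Day 1) to end of study, in both arms. Align 9.4 with the same start.
- **14.1:** state that the AE definition applies to all randomised subjects. This is a clarification that removes doubt about undosed controls.
- **14.5:** state that the exclusion does not apply to an event meeting a seriousness criterion, which is then reported under 14.2.2. Record new or worsened cough, dyspnea and desaturation in the eCRF in both arms, with time relative to nebulisation in the active arm, so that 14.5 agrees with 8.1.8.

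The cost is a protocol amendment and some additional eCRF entries. No new patient procedure is needed.

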14.2.2. SAE reporting

SAE's occurring during the entire study period will be reported as below.

All serious adverse events (initial and follow up information) and pregnancies occurring during this study must be reported by the local Principal Investigator within 24 hours after becoming aware of the SAE to:

- The local ethics committee (it is the responsibility of the local PI to report the local SAE's to the local EC)
- HIRUZ CTU of the University Hospital Ghent
- The National Coordinating Investigator (in case of multicenter studies)
The company Partner Therapeutics that provides the IMP

This reporting is done by using the appropriate SAE form. For the contact details, see below.

14.2.3. SUSAR reporting

In case the Coordinating Investigator, in consultation with HIRUZ CTU, decides the SAE is a SUSAR (Suspected Unexpected Serious Adverse Reaction), HIRUZ CTU will report the SUSAR to the Central EC and the FAMHP within the timelines as defined in national legislation. The Coordinating Investigator reports the SUSAR to all local PI's.

In case of a life-threatening and fatal SUSAR the entire reporting process must be completed within 7 calendar days. In case of a non life-threatening SUSAR the reporting process must be completed within 15 calendar days.

14.4. Flowchart Reporting

Type of Adverse Event	Action to be taken
AE	List all AE's per subject in the patient's file and add this information to the CRF.
SAE	Notify to HIRUZ CTU within 24 hours after becoming aware of the SAE + add the SAE to a list that will be reported yearly (see section 13.8)
SAR	Notify to HIRUZ CTU within 24 hours after becoming aware of the SAE → HIRUZ CTU will submit to the central EC

	→ study team informs company that provides the IMP
SUSAR	Notify to HIRUZ CTU within 24 hours after becoming aware of the SUSAR → HIRUZ CTU will submit to the central EC. → HIRUZ CTU will submit to the FAMHP → study team informs company that provides the IMP

In case the (SU)SAR occurs at a local participating site, the local PI or study team should also contact:

- The local Ethics Committee
- The Co-ordinating Investigator

14.5. Events, excluded from reporting

COVID-19 infection is a very recent syndrome, on which few data are available. Normal symptoms and natural disease course symptoms that will not be reported as adverse events are dyspnea, coughing, malaise, fever, drop in oxygen saturation, progression to respiratory failure, progression to ARDS, severe drop in blood pressure in the ICU, progression to multi-organ failure.

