3.2. Secondary Objectives

- to study if early intervention with sargramostim is safe (number of AEs/SAEs)
- to study if early intervention with inhaled sargramostim affects clinical outcome defined by
 Duration of hospital stay
 Mean and median change in 6-point ordinal scale between day 1 and day 6
 Mean and median change in clinical sign score between day 1 and day 6
 Time to clinical sign score <6 maintained for 24h
 Mean and median change of SOFA score between day 1 and day 6 or between day 1 and day 10.
 Mean and median change NEWS2 score between day 1 and day 6 or between day 1 and day 10.
 Time to NEWS2 score less than 2 for at least 24h
- to study if early intervention with sargramostim affects the rate of nosocomial infection
- to study if early intervention with inhaled sargramostim affects progression to mechanical ventilation and/or ARDS
- to study if treatment with sargramostim affects all cause mortality rate at 28 days and 20 weeks post inclusion
- to study if treatment with sargramostim affects features of secondary haemophagocytic lymphohistiocytosis, as defined by Hs score (temp, organomegaly, cytopenia, triglycerides, fibrinogen, ferritin, AST and known immunosuppression)
- to study if treatment with sargramostim has a favourable effect on long term 10-20 week follow up

4. End Points + Time Points

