On days 1-5, patients in group A will inhale sargramostim 125mcg twice daily for 5 days as a nebulized inhalation using a Philips InnoSpire Go portable mesh nebulizer on top of standard of care. This device is a handheld mesh nebulizer that can be fitted with a facial mask. Patients will be instructed prior to receiving the first dose on how to use this simple device, by a physician. This procedure is finished in 5-10 minutes, and will be performed twice daily, in the morning (between 6 a.m. and 11 a.m.) and evening (between 6 p.m. and 11 p.m.).

Upon progression of disease requiring initiation of non-invasive or invasive mechanical ventilatory support within the 5 day period, in patients in the active group, inhaled sargramostim will be replaced by intravenous sargramostim 125mcg/m² body surface area once daily until the 5 day period is reached. This administration will occur via a centrally placed catheter or peripheral catheter, that will be in place as part of routine medical care at the ICU.

On a final clinical visit between week 10-20 an additional serum tube (5ml) and an EDTA tube (10 ml) will be taken in selected centers.

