Suspected Unexpected Serious Adverse Reaction (SUSAR)	
A serious adverse reaction, the nature and severity of which is not consistent with the information about the medicinal product in question set out:
 
 • in the case of a product with a marketing authorisation, in the summary of product characteristics (SmPC) for that product • in the case of any other investigational medicinal product, in the investigator's brochure (IB) relating to the study in question

Attribution definitions

An adverse event is considered associated with the use of the drug if the attribution is possible, probable or definitive.

Not related

An adverse event which is not related to the use of the drug.

Unlikely

An adverse event for which an alternative explanation is more likely - e.g. concomitant drug(s), concomitant disease(s), and/or the relationship in time suggests that a causal relationship is unlikely.

Possible

An adverse event which might be due to the use of the drug. An alternative explanation - e.g. concomitant drug(s), concomitant disease(s), - is inconclusive. The relationship in time is reasonable; therefore the causal relationship cannot be excluded.

Probable

An adverse event which might be due to the use of the drug. The relationship in time is suggestive (e.g. confirmed by dechallenge). An alternative explanation is less likely - e.g. concomitant drug(s), concomitant disease(s).

Definitely

An adverse event which is listed as a possible adverse reaction and cannot be reasonably explained by an alternative explanation - e.g. concomitant drug(s), concomitant disease(s). The relationship in time is very suggestive (e.g. it is confirmed by dechallenge and rechallenge).

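### Section 14.5 excludes serious disease-course events from adverse event reporting with no written exception for serious or suspected drug-related cases, in conflict with 14.1 and 14.2

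*Protocol*

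**What the plan says.** Section 14.5 of the protocol, headed as events excluded from reporting, opens its list with "Normal symptoms and natural disease course symptoms that will not be reported as adverse events are dyspnea, coughing" and ends it with "progression to respiratory failure, progression to ARDS, severe drop in blood pressure in the ICU, progression to multi-organ failure". The list carries no condition on seriousness, outcome or attribution.

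The rest of section 14 sets general duties. Section 14.1 counts any untoward occurrence in a treated subject as an adverse event, whether or not the product caused it. It makes an event serious if, among other criteria, it leads to death, is life-threatening or prolongs hospitalisation. It treats a reasonably suspected causal link as enough for an adverse reaction, and on attribution it says: "An adverse event is considered associated with the use of the drug if the attribution is possible, probable or definitive". Section 14.2.1 requires all adverse events to be recorded in the patient file and the CRF. Section 14.2.2 says: "All serious adverse events (initial and follow up information) and pregnancies occurring during this study must be reported by the local Principal Investigator", with a 24-hour limit.

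Section 3.2 states the safety objective as "to study if early intervention with sargramostim is safe (number of AEs/SAEs"), and section 4.2 makes the comparison of AEs and SAEs between groups A and B a secondary endpoint because safety data in COVID-19 are lacking. Section 2.3 likewise says there are none for this drug in this disease.

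**The concern.** Respiratory failure, ARDS, severe hypotension and multi-organ failure are serious events that can be expected in patients enrolled with acute hypoxic respiratory failure. If 14.5 is applied as written, such an event is not an adverse event, so it cannot become an SAE, an adverse reaction or a SUSAR, even where an investigator suspects the drug. Two things are then at stake. The SAE comparison that is meant to answer the safety objective loses these events in both arms. Case-by-case reporting within 24 hours, and the 7- or 15-day SUSAR timelines, lose them too. If some sites follow 14.5 and others 14.2.2, the SAE counts also become inconsistent between sites.

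**Working it through.** **1. The sections side by side.** Take one case: multi-organ failure that is life-threatening and that the investigator rates as possibly related.

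| Protocol section | What follows for this case |
|---|---|
| 14.1, adverse event | An AE; the definition does not depend on cause |
| 14.1, seriousness | An SAE, because it is life-threatening |
| 14.1, attribution | Associated with the drug, because possible is enough |
| 14.2.1 | Recorded in the patient file and CRF |
| 14.2.2 | Reported within 24 hours |
| 14.5 | Not reported as an adverse event |

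The first five rows agree with each other; the last does not. Sections 14.1, 14.2.1 and 14.2.2 do not mention 14.5, and 14.5 mentions none of them, so no order of precedence is written.

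**2. Which routes close.** In 14.2.3 the SUSAR decision is taken on a reported SAE. In 14.4 the SAR and SUSAR rows start from a notification to the clinical trial unit. Under 14.7 the annual safety report compiles SAEs. An event that never becomes an AE enters none of these.

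**3. Non-serious items.** The list also contains dyspnea and coughing. Section 8.1.8 names cough and dyspnea among effects already observed with the aerosolised drug. An attribution step is therefore needed for non-serious items as well.

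**4. What remains visible by arm.** Section 4.2 has progression to ventilation and/or ARDS, the 6-point ordinal scale, SOFA (Day 1 to Day 6 or Day 10) and mortality at 4 and 20 weeks. Section 12.2 lists deaths with cause by group. The notes to 9.4 show that SOFA uses mean arterial pressure, platelets, bilirubin, creatinine, coma score and oxygenation. These are trial analyses. None sends an individual case to the sponsor, ethics committee or authority.

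**5. Scale.** The only figure in the protocol near these events is in 7.1.1: "It is estimated that some 30% of patients might deteriorate and require non-invasive or invasive mechanical ventilation".

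- Per arm: 0.30 × 40 = 12, which reproduces the protocol's 12.
- Both arms: 2 × 12 = 24.

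This is not a count of 14.5 events. For the active arm the 30% refers to non-invasive or invasive ventilation, and for controls to mechanical ventilation or ARDS. Ventilation itself is not on the 14.5 list, and a listed event can occur outside this group. As an illustration, suppose each of the 24 had one listed event meeting a seriousness criterion. Then 0 would be reported as SAEs if every site followed 14.5, 24 if every site followed 14.2.2, and some number in between if practice were mixed.

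**The case against.** The best defence is that 14.5 is a specific carve-out from a general duty, and that excluding expected disease events while measuring them as endpoints is a legitimate design choice. It can add that the list is confined to the natural course of the disease, so an event attributed to sargramostim is arguably not on it, and that death is not listed at all. Part of this stands: 14.5 can be read that way. But it classifies named events as disease course and gives no attribution step, so a site has nothing to tell it which reading applies. If the narrower reading is meant, it has to be written.

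Several stronger readings are tempting and should not be drawn.

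- **That 14.5 expressly removes fatal or drug-related events.** It does not say so; this is inferred from a missing exception.
- **That the trial could not show that the drug worsens the disease.** The channels in step 4 of the working remain. A purely hypothetical doubling of progression, 24 of 40 against 12 of 40, would give a Fisher exact p of 0.013 on the progression endpoint itself. What is lost is case-level reporting and the SAE comparison, not all detection.
- **That harm would surface only at the final analysis.** Section 14.6 foresees a DSMB. The protocol does not say what data it sees, so neither reassurance nor alarm follows.
- **That intravenous drug goes only to ventilated ICU patients, exactly where hypotension is exempt.** Section 9.2 does describe a catheter "that will be in place as part of routine medical care at the ICU". However, 1.6, 3.1 and 5.1 let progressive active-arm patients have it from Day 6 on the physician's assessment without stating a ventilation condition, and 5.1 also admits controls developing ARDS.
- **That the sHLH objective marks a recognised drug harm.** Section 4.2 presents sHLH as a feature of COVID-19.

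**Conclusion.** The conflict is real and rests on the text. Section 14.5 is unconditional, while 14.1, 14.2.1 and 14.2.2 require the opposite for events that are serious or suspected to be drug-related. Applied as written, 14.5 takes these events out of the A-versus-B SAE comparison and keeps them from the SAR/SUSAR route, for a drug with no stated COVID-19 safety data. Applied unevenly, it makes SAE counts depend on which section a site follows. These are alternative consequences of alternative readings and do not both hold at one site.

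The size cannot be computed from the protocol. The 12 per arm expected to deteriorate gives an order of magnitude only, on the assumption that this group largely overlaps the excluded events.

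**What to change.** Reconcile 14.5 with 14.1 and 14.2 in an amendment, and cross-refer the sections.

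- Limit the exclusion to listed events that are non-serious and judged not related or unlikely related.
- Report a listed event that meets a 14.1 seriousness criterion as an SAE under 14.2.2. Assess it under 14.2.3 if causality is at least possible and the event is unexpected.
- Record a non-serious listed event rated at least possible as an AE. Attribution alone does not make it serious; otherwise a mild, possibly related cough would become a 24-hour report.
- Enter every listed event with its date on the eCRF in both arms from Day 1, and tabulate these by arm beside the AE and SAE counts. Day 1 matters because 14.2.1 starts AE recording at the first drug administration, which a control patient may never have.

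The cost is a short amendment, an eCRF entry, and more SAE forms and site paperwork. The 24 patients expected to deteriorate are a rough guide to the extra forms; the number could be higher, since listed events also occur outside that group. Treatment and sample size do not change.
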